### **4.2 Exclusion Criteria**

- Subjects with contraindications to immune checkpoint therapy, as follows:

CONFIDENTIAL

- Interstitial lung disease that is symptomatic or may interfere with the detection and management of suspected drug-related pulmonary toxicity.
- Prior organ allograft or allogeneic bone marrow transplantation.
- Pre-existing thyroid abnormality with thyroid function that cannot be maintained in the normal range with medication.
- Active autoimmune disease, except for vitiligo, type 1 diabetes mellitus, asthma, atopic dermatitis, or endocrinopathies manageable by hormone replacement; other autoimmune conditions may be allowable at the discretion of the principal investigator.
- Condition requiring systemic treatment with either corticosteroids.
  - Systemic steroids at physiologic doses (equivalent to dose of oral prednisone 10 mg) are permitted. Steroids as anti-emetics for chemotherapy are strongly discouraged
  - Intranasal, inhaled, topical, intra-articular, and ocular corticosteroids with minimal systemic absorption are permitted.
- Pregnant women, women planning to become pregnant and women that are nursing.

#### **4.3 Subject Recruitment**

Subjects will be recruited from the Oncology practices at Penn Medicine. The treating radiation oncologist or medical oncologist will approach and inform the patient about the study, thereby initiating the informed consent process. If the patient expresses interest in the study, the treating radiation oncologist or medical oncologist will contact a qualified member of the research team in the Radiation Oncology Department at the University of Pennsylvania and request availability for enrollment. A qualified member of the research team will initiate the formal consent process. This person will interview the potential subject with privacy considerations, explain the requirements of the study and provide a copy of the Informed Consent Form. The person obtaining consent will state the volunteer nature of research and advise the subject to take sufficient time to discuss the study if necessary before making their decision to sign the informed consent document. If a decision to participate is made, the informed consent form is signed. A series of questions will be asked by the person obtaining consent to verify patient eligibility. After eligibility is established, a subject study number will be issued. Eligibility is confirmed with the study investigator or delegate. All members of the research team will have successfully completed patient oriented research training. The consent process can be completed in person or via Telemedicine per University of Pennsylvania Health Systems telemedicine policy and procedures.

In addition, this trial will be listed on our web site as a formal protocol and information of its availability will be made known to treating professionals throughout our satellites and referring physicians.

#### **4.4 Duration of Study Participation**

The duration of the study is approximately 22-25 weeks, from the time of pre-trial assessment through the final end-of-study visit. The duration of the intervention phase of the study is approximately 20-23 weeks: 8-12 weeks for nivolumab monotherapy, 8-12 weeks for continued nivolumab monotherapy vs. RT plus nivolumab, with 3 weeks allowed for RT simulation and planning. An additional 8-12 weeks is appended for patients undergoing additional RT.

#### **4.5 Total Number of Subjects and Sites**

Recruitment will end when 25 subjects are enrolled with lesions that are measurable as defined in section 6.3.2. Based on published CR rates,[2, 3] it is expected that the induction CR rate in this study population is expected to be approximately 10%.

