### **8.4 Primary Endpoint**

The primary endpoint is the overall CR rate, defined as the total number of CRs after nivolumab induction, plus the total number of CRs after RT + continued nivolumab in those patients with <CR after induction, divided by the total number of patients treated on the study. The Cheson criteria will be used to score response.

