#### **8.8 Plans for Data Analysis**

1. Baseline and demographic characteristics will be summarized by standard descriptive statistics (including mean and standard deviation for continuous variables such as age and frequency and percentage for categorical variables such as gender).
2. The overall CR rate and 95% exact confidence interval will be calculated. Following an intent to treat analysis, all patients who received at least 1 dose of nivolumab are included in the analysis of the primary endpoint. Based on an exact binomial test, the number of patients with CR will determine whether the null hypothesis will be rejected (see Sample Size/Power below).
3. The nivolumab induction CR rate and post-RT + continued nivolumab CR rate and 95% confidence intervals will also be calculated.
4. Time to best response and duration of best response will be calculated and summarized separately for CR, PR, SD and PD patients.
5. Progression free survival, overall survival and disease-free survival will be estimated by the Kaplan-Meier method. Disease free survival will be computed by landmark analysis for two distinct groups: 1) DFS from week 8, for patients who achieved induction CR and 2) DFS from week 16, for patients who achieved CR after RT + nivolumab.
6. All subjects entered into the study will have detailed information collected on adverse events for the overall study safety analysis. Toxicities will be graded and tabled separately by induction nivolumab, post-induction nivolumab or post-induction RT + continued nivolumab.

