## 8.9 Sample Size/Power

With 25 patients, there is 81% power to detect a difference of 20% assuming a null hypothesis that the CR rate = 10% versus an alternative hypothesis that the CR rate = 30% using a one-sided exact test with a 5% significance level. We will reject the null hypothesis if 6 or more of 25 patients achieve a CR. The actual significance level for this exact test procedure is 3%.

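### Recruitment stops at 25 enrolled subjects but the primary analysis counts only dosed patients, and undosed enrollees are not replaced, so the stated 81% power holds only if all 25 are dosed (minor)

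*Combined protocol and SAP*

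**What the plan says.** Four sections of the combined protocol and SAP bear on this, and both copies of the protocol in the file agree.

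- **4.5 (Total Number of Subjects and Sites)** gives the stopping count: "Recruitment will end when 25 subjects are enrolled with lesions that are measurable as defined in section 6.3.2".
- **4.3 (Subject Recruitment)** ties the subject number to eligibility, not to first dose: "After eligibility is established, a subject study number will be issued". Section 6.1 has screening finished before nivolumab starts.
- **8.4 and 8.8** give the analysis count. The complete responses are "divided by the total number of patients treated on the study", and "all patients who received at least 1 dose of nivolumab are included in the analysis of the primary endpoint".
- **8.9 (Sample Size/Power)** reports 81% power for 25 patients, for complete response (CR) rates of 10% (null) against 30% (alternative), "using a one-sided exact test with a 5% significance level". The decision rule is: "We will reject the null hypothesis if 6 or more of 25 patients achieve a CR".

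Neither copy contains a rule for replacing enrolled subjects who are never dosed, or an allowance for them in the sample size.

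**The concern.** The recruitment rule counts one set of people and the analysis another. Enrolment and first dose are separate events, and 6.5 lets a subject withdraw consent at any time, or be withdrawn if enrolment proves inappropriate. A subject lost between the two events takes one of the 25 places and then drops out of the denominator. Because nobody takes the vacated place, the primary test runs on fewer than the 25 patients for which 8.9 states its power.

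What is at stake is the chance of detecting a true 30% CR rate. The trial has one arm, no interim analysis and a single count that decides the primary result, so a smaller number of patients feeds directly into the power of that one test.

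**Working it through.** **Inputs.** Null CR rate 0.10, alternative 0.30, one-sided exact test at 5%, N = 25, reject at 6 or more CRs (all from 8.9). The analysed N is the number dosed (8.4, 8.8). The number of undosed enrollees is not in the documents; I take 1, 2 and 3 as an assumed range.

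**Formula.** For N analysed patients and cut-off c,

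P(X ≥ c | N, p) = 1 − Σ (x = 0 to c − 1) C(N, x) p^x (1 − p)^(N − x).

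The attained significance level uses p = 0.10 and the power uses p = 0.30.

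**Step 1: reproduce the plan.** With N = 25 and c = 6, the level is 0.0334 and the power 0.8065. Section 8.9 states 3% and 81%, so both figures reproduce.

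**Step 2: remove undosed enrollees, keeping the cut-off of 6.**

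| Undosed of 25 enrolled | N analysed | Attained level | Power at 30% |
|---|---|---|---|
| 0 | 25 | 3.34% | 80.7% |
| 1 | 24 | 2.77% | 77.1% |
| 2 | 23 | 2.26% | 73.1% |
| 3 | 22 | 1.82% | 68.7% |

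The successive losses are 80.7 − 77.1 ≈ 3.5 points (from unrounded values), 77.1 − 73.1 = 4.0 points and 73.1 − 68.7 ≈ 4.5 points (from unrounded values).

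**Step 3: could a lower cut-off recover the power?** No. A cut-off of 5 has a level of 5.2% at N = 21, 8.5% at N = 24 and 9.8% at N = 25, all above 5%. The smallest cut-off that respects the 5% level is 6 at every N from 21 to 27; at N = 27 its level is 4.71%.

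**Step 4: does the choice of denominator matter?** Suppose the undosed subject is kept among the 25 and counted as a non-responder. Rejection then still needs 6 CRs from the 24 dosed patients, and P(X ≥ 6 | 24, 0.30) is again 77.1%. The power falls because one fewer patient is treated. Redefining the denominator would not restore it; replacing the subject would.

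**The case against.** The case for leaving the plan alone has several parts.

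- **Non-dosing may be rare.** Eligibility requires that nivolumab be clinically indicated (4.1), and 1.2 describes it as a standard of care for select patients, so enrollees are mostly people already due to receive it. This stands. The documents give no rate, and 25 enrolled and 25 dosed is a quite possible outcome.
- **The loss is modest.** The first undosed subject costs about 3.5 points. Section 8.9 reports 81% as a result and does not set 80% as a requirement, so crossing 80% breaches nothing in the plan. This also stands.
- **The test still works at other N.** Section 8.8 names an exact binomial test, and 8.9 fixes the null, the side and the level. The cut-off for any N follows from these, and it is still 6 throughout the assumed range. A reader might infer that the decision rule becomes undefined or invalid if N is not 25. The documents do not support that.
- **Over-run is remote.** A reader might also infer the opposite risk: dosed subjects without measurable lesions would sit outside the 25 but inside the denominator, and the cut-off of 6 might then exceed the 5% level. That happens only from N = 28 (level 5.50%). It would need three dosed subjects who fail the inclusion criterion of at least two measurable sites (4.1), although 12.4 requires every subject to meet all inclusion criteria. I do not raise this as a concern.

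What survives is the missing replacement rule, together with a stopping count that does not match the analysis set.

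**Conclusion.** The point holds as a minor one. The 81% in 8.9 is right for 25 analysed patients, but the recruitment rule in 4.5 does not secure 25 analysed patients. If one, two or three enrollees are never dosed, power at a 30% CR rate is about 77%, 73% or 69%. These figures rest on the assumed number undosed and on the 10% and 30% rates in 8.9.

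It would be wrong to read this as a threat to the validity of a positive finding. With fewer than 25 patients the attained level drops from 3.3% to between 1.8% and 2.8% over the assumed range. The cost is a greater chance of missing a real effect.

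**What to change.** Replace the stopping sentence in 4.5 with: *Recruitment ends when 25 subjects have received at least one dose of nivolumab; enrolled subjects never dosed are replaced.*

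The stopping count then matches the analysis set in 8.8, and the level of 3.3% and power of 80.7% apply as designed. Measurable disease need not be repeated there, because it remains an inclusion criterion in 4.1. Section 8.9 needs no change: a table of cut-offs for other N would add nothing, since the cut-off follows from the stated test.

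The cost is one sentence and at most a few extra consents and screenings. No more than the planned 25 patients are treated.

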#### **4.6 Vulnerable Populations:**

Vulnerable populations are not specifically included in this research study. We do not anticipate enrolling prisoners.

CONFIDENTIAL

## 5 Study Intervention

### 5.1 Description

Nivolumab is a highly selective, humanized monoclonal antibody (IgG4) that blocks PD-1. Nivolumab was tested as single-agent monotherapy in a Phase II trial of 80 HL patients who progressed after stem cell transplant and BV, demonstrating 9% CR, 58% PR, and 23% SD rates with an impressive 6 month PFS of 76.9%. [3] Nivolumab is now FDA-approved for r/r HL. The combination of nivolumab with radiation is based on the observation that RT can enhance immunomodulators in lymphoma. [5-7] Based on preclinical sequencing experiments, [6, 9] RT will be given after the first response assessment after 8-12 weeks of nivolumab in patients with less than CR. RT will be given in 2 fractions of 4 Gy each, to be delivered to an index site using an involved site paradigm.

### 5.2 Intervention Regimen

#### 5.2.1 Nivolumab Administration

Nivolumab (3 mg/kg) will be administered as an IV infusion on day 1 and continued per standard of care and institutional practices. Nivolumab will be given in the outpatient oncology units of the University of Pennsylvania Health System. Patients will be monitored in the clinic after the infusion and discharged when deemed stable by the clinical staff. Medications to treat hypersensitivity reactions should be immediately available, including epinephrine, diphenhydramine, methylprednisolone and nebulized albuterol.

#### 5.2.2 Radiotherapy Administration

Involved-site radiotherapy will be administered after the first response assessment following induction nivolumab. RT will be delivered in the Department of Radiation Oncology. All subjects will be immobilized as needed in a custom designed device in the appropriate position to isolate the index lesion. Radiotherapy treatment planning using CT or PET/CT scanning will be required to define the gross target volume (GTV) and clinical target volume (CTV). All tissues to be irradiated must be included in the CT scan. Planning CT scan will be done at 3 mm intervals from encompassing the region of interest with sufficient margin for treatment planning.

#### 5.2.3 Target Contouring

Gross Tumor Volume (GTV) is defined as all known gross disease encompassing the selected index lesion. The GTV will consist of the index lesion as visualized on CT and PET. A CTV (or ITV, internal target volume) will be defined using an involved site radiation therapy paradigm, and can include elective target volume at the discretion of the treating radiation oncologist. Volumes must be designed to allow for an additional measurable lesion to be excluded from the radiated volume (non-target lesion).

Planning Target Volume (PTV) will be defined as per the convention for photon beam radiotherapy. A 3-dimensional margin will be created on the GTV or IGTV (if available) to allow for daily set-up variance.

#### 5.2.4 Normal Structures

Organ at risk volume (OAR) is contoured as visualized on the planning CT scan depending on the location of the index lesion.

#### 5.2.5 Dose Fractionation

All patients will be given 2 fractions of 4 Gy each over a period of 2-4 days, depending on the radiation oncology schedule, to the PTV as defined above.

#### 5.2.6 External Beam Equipment and Beam Delivery

Radiation treatments will be administered at the University of Pennsylvania Department of Radiation Oncology. A radiation oncologist will check the first film on all fields. All set-up films will be permanently filed for all subjects.

CONFIDENTIAL

### 5.2.7 Quality Assurance

Daily portal films or online radiographic imaging will be performed during therapy. All periodic and patient-based quality assurance for patient treatment will conform to established Penn Radiation Oncology Department standards and all treatment plans will be reviewed at weekly quality assurance meetings (chart rounds).

### 5.3 Investigational Product

Clinical supplies of nivolumab will be provided by Bristol-Myers Squibb as part of standard of care as summarized below

#### Product Description.

Product Name and Potency	Dosage Form
NIVOLUMAB 3mg/kg	Solution for Injection

### 5.4 Storage

Clinical supplies must be stored in a secure, limited-access location under the storage conditions specified on the label.

### 5.5 Preparation and Packaging

Clinical supplies will be affixed with a clinical label in accordance with regulatory requirements.

This trial is open-label; therefore, the subject, the trial site personnel, the Sponsor and/or designee are not blinded to treatment. Drug identity (name, strength) is included in the label text; random code/disclosure envelopes or lists are not provided.

## 6 Study Procedures

	Eligibility	Pre-response Assessment			Post-response Assessment				
		Week (from start of nivo.)			Week				
		1	4	8-12	0 (if RT)	1	4, 8	12	FU 
Tests and Observations									
History, PE, VS	X		X	X	X		X	X	X
ECOG Performance Status	X		X	X	X		X	X	X
Toxicity Assessment			X	X			X	X	X
FDG PET/CT	X		X 	X				X 	X 
Laboratory									
Correlative Biomarkers	X	X	X	X	X	X	X	X	
CBC w/ differential	X		X	X	X		X	X	X
Complete metabolic panel	X		X	X	X		X	X	X
Standard-of-care laboratory tests appropriate for nivolumab	X		X	X	X		X	X	X
Pregnancy Test	4				X 				

Research FDG PET/CT at time of week 1 correlative biomarkers blood draw.

Week 8-12.

As clinically indicated.

CONFIDENTIAL

Pregnancy test is required only for women of child-bearing potential. A serum or urine test can be performed.

### **6.1 Screening**

An investigator must explain the nature of the study protocol and risks associated with the protocol in detail to the subject. The subject must sign and date the written informed consent prior to study participation. Informed consent process must be obtained before protocol procedures are performed. If a procedure required for screening was performed prior to signing the informed consent and the procedure meets the time limits of the protocol, this procedure may be used for the screening evaluation.

Screening will be completed prior to starting nivolumab.

Screening includes:

- Informed consent.
- Confirmed ECOG performance status of 0, 1 or 2.
- Complete medical history.
- Standard-of-care laboratory tests appropriate for nivolumab.
- Documentation of pathological, imaging, and clinical confirmation of relapsed/refractory Hodgkin lymphoma.

### **6.2 Study Intervention Phase**

#### **6.2.1 Procedures Prior to Protocol Therapy**

The following tests must be performed within 6 weeks of enrollment and prior to starting nivolumab.

Baseline standard of care procedures that include:

- Standard-of-care history, physical examination, and laboratory tests as clinically indicated
- FDG-PET
- Correlative biomarkers

#### **6.2.2 FDG PET/CT Imaging Visits**

The following procedures will be done at each imaging session, as per routine clinical practice for FDG PET/CT imaging.

All women of child-bearing potential will be asked on the day of the PET/CT scan if they might be pregnant; this is a standard question for all patients who will be undergoing PET/CT scans due to the radiation exposure associated with the scan. If the patient is unsure about whether she might be pregnant then a urine pregnancy test will be performed prior to the injection of FDG.

The patient will be made comfortable in a preparatory room. Approximately 15 mCi of FDG will be administered according to the standard procedures used for clinical FDG PET/CT at the Hospital of the University of Pennsylvania. All patients will undergo a skull base to thighs PET/CT scan starting at approximately 60 minutes after FDG injection. A brief low-dose CT scan will be acquired according to standard PET/CT imaging procedures; this is used for attenuation correction and anatomical localization of findings in the PET scan. This can be performed either before or after the PET transmission scan. There are no separate diagnostic CT scans performed as part of this research.

A total of at least 3 FDG PET/CT exams will be performed as follows:

- Baseline: A clinical baseline FDG PET/CT will be obtained no more than 6 weeks prior to initiation of nivolumab to assess baseline, pre-therapy tumor glycolytic activity. This exam is clinical standard of care for staging of disease prior to initiation of a new line of therapy and would be performed even if the patient was not enrolled in the study. This exam may occur prior to consent and enrollment in this study.

CONFIDENTIAL

This material is the property of the University of Pennsylvania.

- **Post-therapy:** Approximately 1 week following the start of nivolumab, a post-therapy FDG PET/CT will be obtained. This PET/CT will be obtained for study purposes, to assess glycolytic activity at sites of metastatic disease at an early time point. The results from this scan will not be reported to the participant, and will have no impact on the treatment decisions made by the treating physician.
- **Response assessment:** At weeks 8-12 after the start of nivolumab, FDG PET/CT will be obtained for response assessment. For patients undergoing radiotherapy, an additional FDG PET/CT will be obtained at weeks 8-12 after the delivery of radiation. Subsequent FDG PET/CT(s) will be obtained as clinically indicated in follow-up.

Adverse events that are grade 3 or higher will be recorded post injection of the radiotracer to the completion of the imaging exam.

### 6.2.3 Procedures During Nivolumab Administration

As per standard of care, patients will be seen by a physician, advanced practice provider, or registered nurse prior to nivolumab infusion and a toxicity assessment will be performed. The following laboratories will be performed prior to infusion every 4 weeks:

- Standard-of-care laboratory tests appropriate for nivolumab
- Correlative biomarkers

Patient records will be reviewed by the study coordinator in conjunction with the PI to determine toxicities, including the grade and attribution to nivolumab.

### 6.2.4 Procedures During Radiation

As per standard of care, patients will be seen by a physician once while receiving radiation treatment, and a toxicity assessment will be performed. Patient records will be reviewed by the study coordinator in conjunction with the PI to determine toxicities, including the grade and attribution to radiation.

Prior to initiation of radiation, a blood sample will be collected for correlative biomarkers.

## 6.3 Follow Up Phase of the Study

### 6.3.1 Image Interpretation

Static images will be reconstructed using standard procedure and analyzed by visual inspection and standardized uptake value (SUV) analysis. The tumor avidity, as estimated by the SUVmax, of up to 6 lesions will be measured on each FDG PET/CT scan. Patients will also be grouped based on a positive flare response (greater than 20% increase in SUVmax) or negative flare response (less than 20% increase in SUVmax).

